#### **Study Staff:**

The **Clinical Research Nurse** is a staff member of the Emergency Department trained in the study measures. They will be responsible for approaching and consenting participants. They will complete the screening measures in the ED.

The **Research Coordinator** is responsible for randomizing the participants, scheduling the participants' initial study visits, emailing electronic REDCap surveys, completing the enhanced usual care telephone visits, and overseeing the operation of the study. The research coordinator is trained to conduct the screening sessions if the clinical research nurse is unavailable.

The **Research Assistant** is responsible for completing the 6-week and 24-week study visits and is trained in the administration and scoring of the measures. The RA is also responsible for reimbursing participants. They are blinded to the intervention and group assignment.

The **Therapist** is responsible for scheduling and administering the F-SPS intervention with participants, and communicating with UC providers.

All staff will be certified in TCPS-II and GCP training, and fully trained on study measures that they are responsible for implementing. Certificates and training logs will be stored in an essential documents binder in the coordinators office.

#### **Measures:**

##### ***Primary Outcome Measures: Completed by Patient***

The **Suicide Ideation Questionnaire Junior High School Version (SIQ-Jr)** is a 15-item measure self-report of suicide ideation (e.g., thoughts about death and dying) completed by the patient. Items are scored from 0 to 6. The measure takes 5 minutes, and is completed in-person at baseline, week 6 and week 24.

The **Suicide Behavior Questionnaire – Revised (SBQ-R)** is a 4-item self-report questionnaire that measures suicide behaviour (i.e., previous suicide attempts or the likelihood of future attempts) over the

lifetime (at baseline) or over 1 month period (follow-up). The measure takes less than 5 minutes, and is completed in-person at baseline, week 6 and week 24.

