This study will examine the effectiveness of a previously-piloted, ED-based suicide prevention intervention using a randomized clinical trial design. We will determine whether our patient- and Family-centered Suicide Prevention Strategy added to usual care (F-SPS + UC) is more effective than enhanced usual care (EUC) in reducing suicide-related behaviors in 128 youth at high-risk of suicide. F-SPS is a 6-week, outpatient program that teaches participants to identify and challenge the thoughts, feelings and conflicts that suicidal youth experience, and teaches them skills to manage impulses effectively. Piloting by the SickKids team has established the feasibility and acceptability of the intervention. Enhanced usual care consists of 6 weekly telephone calls to ensure that the participant has connected with community resources suggested by the ED team and provide additional resources as needed. Rigorous evaluation will investigate the intervention for an effect on suicide-related behavior and mental health crises (primary outcomes), mental health symptoms, patient/family functioning, economic costs, scale up/implementation feasibility and intervention fidelity (secondary outcomes). The proposed study is novel, in that it is the **first clinical trial of a youth suicide intervention in Canada**; it is efficient, in that it leverages the research-base and therapeutic infrastructure of a highly experienced child health team; and it is important, in that it targets the prevention of recurrent suicide attempts and of suicide, a leading cause of death. This study will be the first step toward developing an effective suicide prevention program that can be scaled-up and implemented across Ontario and Canada, to provide youth at high risk of suicide access to effective, evidence-based treatment, regardless of the community in which they live.

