### **Research Question:**

Among youth 12-18 years of age, presenting with SRB to the ED, does a focused suicide prevention strategy added to usual care (F-SPS + UC) lead to decreased SRB in the 6 month follow-up, as compared with enhanced usual care (EUC)?

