### **Hypothesis**

1. To determine the effect of a Focused Suicide Prevention Strategy added to usual care (F-SPS + UC) on SRB. Hypothesis 1 (H1): Compared with EUC, we hypothesize that the F-SPS + UC will be effective in decreasing SRBs over the 6-month follow up period.
2. To examine the effect of F-SPS + UC on future acute mental health crises (ED and unscheduled health care visits). Hypothesis 2 (H2): Compared with EUC, we hypothesize that participants who

receive the F-SPS + UC intervention will have significantly fewer acute mental health crises.

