### **Procedure:**

The clinical research nurse in the ED will conduct a pre-screen of patients admitted to the ED using the Emergency Department Information System (EDIS), identifying patients within the eligible age range (12 – 18 years old) who present with SRB. A clinical nurse who is a part of the patient's circle of care will ask the youth and parent(s) or caregiver for permission to be approached about research. If the youth and parent(s) or caregiver give permission then the clinical staff will introduce the research nurse who will conduct a screening assessment to determine whether the youth is eligible. The assessment will consist of a clinical interview for psychosis and two self-report measures for suicidal ideation and behaviour. If the youth is eligible for the study then the nurse will alert the study research coordinator. . If the patient is eligible the clinical research nurse will review the consent or assent with the youth and parent(s), who will consent separately for their involvement with the Family-based component of the intervention. If both the youth and parent(s) or caregiver sign consent forms, then they will be enrolled into the study. It will be considered as refusal if one of the two parties does not consent, and they will not be enrolled in the study.

The study coordinator will contact the participant by telephone within a business day of their discharge from the ED to review the study procedures and to book their study assessment visits at baseline, to occur within two weeks of the index ED visit. They will also book their study visits six weeks post-randomization, and 24 weeks post-randomization. The study assessment visits will be completed either at SickKids or at the participant's home, depending on availability. The study coordinator will then randomize the participant to receive either to the F-SPS intervention + UC arm or EUC arm.

The study therapist will contact the participants randomized to receive the F-SPS intervention + UC arm and scheduled for their first treatment. The study coordinator will contact participants randomized to the EUC arm and schedule their EUC first phone call, and will provide resources to the child and family.

The research assistant will be responsible for administering outcome measures at study assessment visits, and will therefore be blinded to treatment allocation. We cannot blind the study coordinator, study therapist or families to treatment allocation.

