In total there are four study visits. Participants will be assessed once by the study nurse at screening (the time of presentation in the ED), once by the study coordinator at baseline, and twice by the research assistant at 6 weeks post-randomization (at post-intervention), and 24 weeks post-randomization. Please see Table 1 for a complete measure administration schedule.

**Treatment allocation (F-SPS+UC or EUC):** Participants will be randomized to either receive the intervention, in addition to usual care (F-SPS+UC), or EUC only. They will be assigned in a 1:1 ratio of F-SPS+UC to EUC.

We will audio record F-SPS sessions if both the youth and the parent(s) or caregiver consent. These sessions will be reviewed by the principal investigators and the study staff in order to ensure fidelity to the treatment model.

In order to determine whether F-SPS+UC or EUC is related to a patient's health care service use, an analysis of participants' emergency room visits and unexpected medical appointments will also be conducted. OHIP numbers will be obtained at consent to link to ICES databases. .

We will recruit 128 adolescents to be randomized (64 adolescents per treatment arm) for this study (see 4.3 "Power Analysis").

**Intervention: F-SPS + UC (i)** is a manualized program that addresses the most common thoughts, feelings and conflicts that suicidal youth experience and teaches coping and safety skills to adolescents and their families. The program is the result of 3-years of development and quality improvement led by the PI ([name]), developed collaboratively with youth, families, and therapists. The program will be administered once weekly over 6 weeks by a trained therapist on an outpatient basis. Sessions consist of 1-hour spent one-to-one with the youth, followed by 1-hour with the youth and parent(s) or caregiver.

The therapist provides the youth and parent(s) or caregiver with a manual to use both during and between sessions. The program and manual address sources of conflict, ways to improve communication and ensure safety. The program resembles the only ED-based adolescent and family programs that have demonstrated effectiveness in decreasing suicidality. It is tailored to address the key concerns of the adolescent or family including mental health, academic problems, social or family conflict, acculturation issues, gender concerns or other stressors.

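### After randomisation the SBQ-R asks about suicide attempts in only two 1-month windows, leaving about 64% of the 24 weeks (63-67%) unasked

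*Protocol*

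**What the plan says.** The Research Question asks whether the intervention will "lead to decreased SRB in the 6 month follow-up", and Hypothesis 1 states that it "will be effective in decreasing SRBs over the 6-month follow up period". The Narrative Summary says the evaluation looks for "an effect on suicide-related behavior and mental health crises (primary outcomes" and adds that "it targets the prevention of recurrent suicide attempts and of suicide, a leading cause of death". The Background criticises an earlier family-therapy trial for, among other things, not capturing attempts, and presents this study as dealing with the weaknesses of previous work.

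Under Primary Outcome Measures, two self-report scales are listed. The SIQ-Jr is described as measuring ideation. The SBQ-R is described as measuring suicidal behaviour, including past attempts, with recall over "lifetime (at baseline) or over 1 month period (follow-up".

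The Procedure section schedules assessments after baseline "twice by the research assistant at 6 weeks post-randomization (at post-intervention), and 24 weeks post-randomization". Table 1 agrees: after randomisation the SBQ-R is marked at weeks 6 and 24 only.

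The Outcomes section names change in SIQ-Jr as the primary outcome. The Power Analysis and Data Analytic Plan assigns Hypothesis 1 to that score.

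**The concern.** The aim is worded as an effect over a period of six months, but the one scale described as asking about attempts looks back only one month from each of two visits 18 weeks apart. A youth who attempts suicide in, say, week 12 and reports accurately at both visits would have no place on the SBQ-R to record it.

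At stake is a basic descriptive result: how many youths in each arm made at least one attempt during follow-up. The recall period and visit schedule are fixed in the protocol. A statistical analysis plan can choose how to analyse the answers, but it cannot supply self-reports for weeks that nobody asked about.

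**Working it through.** The protocol gives no coverage figure, so there is none to reproduce.

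**Inputs**
- Follow-up: 24 weeks from randomisation (Procedure), or 24 x 7 = 168 days.
- SBQ-R after randomisation: day 42 (week 6) and day 168 (week 24) (Measures; Table 1).
- Recall at each: 1 month (Measures). The length of a month is not defined. Assumption: 30 days, with a range of 28 to 31.
- Assumption: visits take place on schedule.
- First SBQ-R: at screening in the ED, before randomisation (Table 1; Procedure).

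**Whole follow-up.** Uncovered share = (168 - 2m) / 168, where m is the length of the month in days.
- m = 30: windows are days 12-42 and 138-168; (168 - 60) / 168 = 108 / 168 = 64.3%.
- m = 28: 112 / 168 = 66.7%.
- m = 31: 106 / 168 = 63.1%.

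**Where the gaps lie (m = 30).** Days 0-12 (12 days) and days 42-138 (96 days); 12 + 96 = 108.

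**Weeks 6 to 24.** This interval has 168 - 42 = 126 days. Uncovered share = (126 - m) / 126.
- m = 30: 96 / 126 = 76.2%.
- m = 28: 98 / 126 = 77.8%.
- m = 31: 95 / 126 = 75.4%.

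**Does another source fill the gap?**

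| Source | What the protocol describes |
|---|---|
| SIQ-Jr | Ideation (Measures) |
| YSR, CBCL | Behavioural, emotional and social problems; 2-week recall at follow-up |
| K-SADS | Not repeated after baseline |
| ICES linkage, diary | ED and unscheduled health visits |
| HCUS | Use and cost of care; baseline and week 24 |
| Usual Care Tracking Survey | Changes in usual care; weeks 1 to 6 |
| Adverse event documentation | All events during enrolment; no structured attempt question described |

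The care-based sources can show an attempt that led to a visit. They miss one that never reached care. Adverse event documentation is not restricted to care, but it depends on what staff come to hear. In weeks 1 to 6 that differs by arm: a therapist spends two hours a week with the F-SPS youth and family, while the comparator receives telephone checks, including calls to the parent. From week 6 to week 24, Table 1 schedules no study contact in either arm.

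**What an added attempt question could show.** With 64 per arm all answering and the same attempt proportion p in each arm, the half-width of the 95% interval for the difference is 1.96 x sqrt(2p(1 - p) / 64). The values of p are assumed and do not come from the protocol.
- p = 0.05: 7.6 percentage points.
- p = 0.10: 10.4.
- p = 0.20: 13.9.
- p = 0.25: 15.0.

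**The case against.** The strongest reply is that no planned endpoint is broken. The Objectives define SRB as ideation together with risk behaviours, not as attempts alone. Hypothesis 1 is tested on the SIQ-Jr at weeks 6 and 24, and no section promises a count of attempts. Short recall at follow-up also looks deliberate: the CBQ, YSR and CBCL likewise move from six months at baseline to two weeks afterwards. All of this stands. It means that the gap limits the description of attempts and leaves the primary conclusion alone. It does not explain how a study said to target recurrent attempts would report them over its stated period.

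A second reply is that attempts will surface elsewhere: "OHIP numbers will be obtained at consent to link to ICES databases", and adverse events are documented throughout enrolment. This stands in part. A reader might infer from the SBQ-R gap that attempts in the unasked weeks go wholly unrecorded, and the documents do not support that. The content of the diary and of the suicide-risk operating procedure is also not shown. What is missing is a uniform question put to every participant.

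A third reply would shrink the gap to about 57%. The Measures section places the first SBQ-R at baseline, a visit "to occur within two weeks of the index ED visit", and the Procedure section does not state clearly whether that visit precedes randomisation. A lifetime form completed after randomisation might then seem to cover the first 12 days: (108 - 12) / 168 = 57%. This does not stand. Table 1 marks the form at screening, and the Procedure section includes self-report measures of suicidal ideation and behaviour in the screening assessment, before consent and randomisation. A lifetime question would also not date an attempt to the days after randomisation.

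**Conclusion.** The point holds as a limit on what the trial can report about attempts. About 64% of the 24 weeks (63-67%) and about 76% of weeks 6 to 24 (75-78%) lie outside any SBQ-R window. These figures rest on the stated 1-month recall, a month of 28 to 31 days, visits on schedule and a first SBQ-R before randomisation. Self-reported attempts over the six months in the Research Question and Hypothesis 1 therefore cannot be fully described.

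A reader might go further and infer that Hypothesis 1 cannot be tested or that the trial is underpowered as a result. The documents do not support that. The test uses the SIQ-Jr, and the sample size of 128 rests on an SIQ-Jr difference of 7 with an SD of 14. The 1-month SBQ-R score also remains a valid comparison between arms at each visit. The change is worth making because it is cheap and cannot be made after the visits have passed.

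**What to change.** Leave the 1-month SBQ-R as it is at weeks 6 and 24. Beside it, add one attempt question: any attempt, how many, and approximate dates. At week 6 it covers the time since randomisation; at week 24 it covers the time since week 6. The blinded research assistant asks it in the same words in both arms, so that ascertainment does not depend on how much contact each arm has had. Report by arm, descriptively, the number and percentage with at least one attempt over the 24 weeks.

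The cost is about a minute at each of two existing visits. No visit is added, and the SBQ-R, the primary test and the sample size do not change. There are two drawbacks to state in the protocol. Recall over 18 weeks is less accurate than recall over one month; asking for approximate dates allows the last month to be set against the SBQ-R. The between-arm difference will also be imprecise, about +/-8 to +/-15 percentage points at assumed attempt proportions of 5% to 25%, so it should carry no formal test.

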***Secondary Outcome Measures: Completed by Child***

The **Clinical Information** form is a 3-item record completed by the clinical research nurse. It captures the date and time of admission, the Canadian Triage and Acuity Scale score of the patient. It is completed at screening by the nurse using the clinical chart.

The **Columbia Impairment Scale – Child (CIS-C)** is a 13-item self-report scale designed to measure functioning on a 5 point Likert scale. This measure is completed by both the child and the parent(s) or caregiver. The measure takes 5 minutes, and is completed through REDcap at baseline, week 6 and week 24.

The **Conflict Behavior Questionnaire– Child (CBQ-C)** is a 20-item self-report scale that has a child report and parent report version that examines the parent-child relationship and measures conflict over a 6 month period at baseline, and over a 2 week period at follow-up. The child report version is to be completed about each parent. The measure takes 5 minutes, and is completed through REDcap at baseline, week 6 and week 24.

The **Life Problems Inventory (LPI)** is a 60-item self-report scale that measures life stressors on a 5 point Likert scale. The measure takes 15 minutes, and is completed through REDCap at baseline, week 6 and week 24.

The **Schedule for Affective Disorders and Schizophrenia for School Age Children, Present and Life Version (K-SADS-PL)** is a semi-structured psychiatric interview designed for use with children and adolescents. Parents and children are asked about current and lifetime history of psychiatric symptoms, including screens for depression, mania and psychosis. The mania and psychosis items take 15 minutes, and are administered by the study nurse at screening visit. The depression interview (DEP-C) takes 20 minutes, and is conducted by the research coordinator at baseline.

The **Feedback Form: Child Version** is an 8-item self-report measure created for this study that includes both quantitative and qualitative items and solicits feedback from youth enrolled in both the F-SPS + UC arm and the ECU arm. The measure takes less than five minutes, and is completed through REDCap at week 6.

The **Youth Self Report (YSR)** is a 112-item self-report measure of behavioral, emotional and social problems over a 6 month period at baseline, and over a 2 week period at follow-up. There are eight subscales: anxious/depressed, withdrawn/depressed, somatic complaints, social problems, thought problems, attention problems, rule-breaking behavior, and aggressive behavior. The measure takes 30 minutes, and is completed through REDCap at baseline, week 6 and week 24.

***Secondary Outcome Measures: Completed by Parent(s) or Caregiver***

The **Child Behavior Checklist (CBCL)** is a 112-item measure, completed by a parent or caregiver, of a child's behavioral, emotional and social problems over a 6 month period at baseline, and a 2 week period at follow-up. There are eight subscales: anxious/depressed, withdrawn/depressed, somatic complaints, social problems, thought problems, attention problems, rule-breaking behavior, and aggressive behavior. The measure takes 30 minutes, and is completed through REDCap at baseline, week 6 and week 24.

The **Children's Affective Lability Scale (CALS)** is a 20 item parent-report instrument that measures difficulties with emotion regulation on 5 point Likert scale. The measure takes five minutes, and is completed through REDcap at baseline, week 6 and week 24.

The **Columbia Impairment Scale – Parent Report (CIS-PR)** is a 13 item scale designed to measure functioning on a 5 point Likert scale. This measure is completed by both the child/adolescent and the parent(s). The measure takes 5 minutes and is completed through REDcap at baseline, week 6 and week 24.

The **Conflict Behavior Questionnaire– Parent Report (CBQ-PR)** is a 20 item scale that has a youth report and parent report version that examines the parent-child relationship and measures conflict over a 6 month period at baseline, and over a 2 week period at follow-up. The measure takes 5 minutes, and is completed through REDcap at baseline, week 6 and week 24.

The basic **demographic information** is collected at the initial assessment. This will include age, sex, date of birth, education, household income, parent occupation, and ethnicity. The measure takes five minutes, and is completed through REDcap at baseline.

The **Evaluation Form: Parent Version** is an 8-item, mixed quantitative and qualitative measure designed for this study that solicits feedback from parents of children enrolled either the F-SPS + UC arm or the ECU arm. This measure takes 5 minutes, and is completed through REDCap at week 6.

The **Health Care Utilization Survey (HCUS)** is a self-report questionnaire of participants' use of available health care services, medication, and the costs associated with those services. There are 11 questions that a participant answers, with an additional follow-up questions depending on answers. It takes 15 minutes, and is completed by the parent(s) or caregiver through REDCap at baseline and 24-weeks.

The **Usual Care Tracking Survey** is an abbreviated version of the Health Care Utilization Survey used to record changes in the patient's usual care over the course of the study. It is administered by the study therapist in-person to the parent(s) at week 1 through 6 for youth who are randomized to the F-SPS + UC, and is administered by the study coordinator over the phone at week 1 through week 6 for those randomized to the EUC arm. The measure takes 5 minutes.

## **Reimbursement**

Participants will receive a \$20 gift card on their final visit of the study. They may also receive community service hours.

**Table 1: Assessment Schedule**

	Session									
	Screening	Baseline	Week 1	Week 2	Week 3	Week 4	Week 5	Week 6	Week 24	
Patient Measures										
K-SADS Mania and Psychosis Screen	x									
Clinical Information	x									
SIQ-JR	x							x	x	
SBQ-R	x							x	x	
Youth Demographic Form		x								
K-SADS DEP_C		x								
CIS-CR*		x						x	x	
CBQ-C*		x						x	x	
LPI*		x						x	x	
YSR*		x						x	x	
Feedback Form: Youth Version								x		
Parent Measures										
Caregiver Demographic Form*		x								
CALS*		x						x	x	
CBCL*		x						x	x	
CIS-P*		x						x	x	
CBQ-P*		x						x	x	
Health Care Utilization Survey*		x							x	
Usual Care Tracking Survey			x	x	x	x	x	x		
Feedback Form: Parent Version*								x		

\* Completed on REDcap Survey

